8.13. Vital Signs

Vital signs will be measured as indicated in Appendix A. Vital signs include temperature, respiratory rate, heart rate, and blood pressure. Patients may be re-evaluated within 2 weeks, at the discretion of the Investigator, if antihypertensive therapy has been started or increased as a result of initial blood pressure measured at Screening. Whenever possible, vital signs will be obtained after at least 5 minutes resting in the supine position or a semirecumbent position. Vital signs will be obtained prior to ECG recordings.

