9.2.3.3. Vital signs

Vital signs and change from Baseline in vital signs will be summarized descriptively at each visit by treatment group. The number and percentage of patients with exceeding pre-defined absolute and relative threshold values (systolic blood pressure increase or decrease from Baseline >25% mmHg, >160 mmHg, or <90 mmHg; heart rate >100 beats per minute or <50 beats per minute; and respiration rate >24 breaths per minute) will be summarized.

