3.6.3 Vital Signs

Vital signs and change from Baseline in vital signs will be summarized descriptively at each visit by treatment group. The number and percentage of patients with exceeding pre-defined absolute and relative threshold values will be summarized. These threshold values are presented in Table 1.

When calculating the percentages for the criterion related to a threshold, the numerator will be the number of subjects with normal baseline with respect to the specific criterion and at least one post-baseline outlier value within the analysis period; and the denominator will be the number of subjects with a baseline and at least one post-baseline assessment within the analysis period.

Table 1 Pre-defined Threshold Value for Vital Signs

Parameter	Criteria
Systolic Blood Pressure (SBP)	>25% mmHg Increased or decreased from Baseline
SBP	>160 mmHg
Heart Rate (HR)	>100 beats per minute
Respiration Rate	>24 breaths per minute
BMI	>10% increased or decreased from Baseline

All vital signs measurements will be listed.

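### SAP Table 1 (section 3.6.3) drops two of the six vital-sign thresholds the protocol pre-defines and adds a BMI criterion with no scheduled follow-up data, while SAP section 5 declares no changes

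*SAP*

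**What the plan says.** Protocol 9.2.3.3 commits to reporting the number and percentage of patients beyond set limits. For blood pressure these are "systolic blood pressure increase or decrease from Baseline >25% mmHg, >160 mmHg, or <90 mmHg". For the other two signs they are "heart rate >100 beats per minute or <50 beats per minute; and respiration rate >24 breaths per minute". The synopsis gives the same list.

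SAP 3.6.3 makes the same commitment but writes out no limits. It says only "These threshold values are presented in Table 1". That table has five rows:

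- SBP change of more than 25% in either direction
- SBP above 160 mmHg
- heart rate ">100 beats per minute"
- respiration rate above 24 per minute
- BMI ">10% increased or decreased from Baseline"

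The section also fixes the percentage base: "the denominator will be the number of subjects with a baseline and at least one post-baseline assessment within the analysis period".

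SAP section 5, reserved for departures from the protocol's analyses, records that there are none.

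**The concern.** The two documents do not ask for the same safety table. The criteria that disappear are both absolute low-side limits, and nothing elsewhere in the SAP brings them back. In their place is a criterion the protocol never mentions and the visit schedule cannot support. The section where such differences should be declared says there are none.

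Safety is the only secondary objective (protocol 2.2, SAP 2.1.2), and vital signs are a named safety assessment (protocol 8.11, SAP 2.3.4). Protocol 1.6 names infection as a risk of anti-inflammatory therapy. Protocol 1.4.3 reports serious cardiac failure and fatal sepsis and cardiac events in the earlier hemodialysis study, none of them attributed to study drug. Low blood pressure and low heart rate are reasonable things to count in that setting. With 12 patients per group, one patient is 1/12, or about 8%, of an arm, so one uncounted patient visibly changes a row.

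**Working it through.** No sample-size or error-rate figure is involved. The check compares the two lists and then asks what the remaining rows can still count.

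**1. Criterion by criterion**

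| Criterion | Protocol 9.2.3.3 and synopsis | SAP 3.6.3, Table 1 |
|---|---|---|
| SBP change >25%, either direction | yes | yes |
| SBP >160 mmHg | yes | yes |
| SBP <90 mmHg | yes | **no** |
| Heart rate >100/min | yes | yes |
| Heart rate <50/min | yes | **no** |
| Respiration rate >24/min | yes | yes |
| BMI change >10% | no | **added** |

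Counting the two-way SBP change once in both documents, the protocol has 6 criteria. The SAP keeps 4, drops 2 and adds 1. Counting its two directions separately gives 7 in the protocol and 5 kept. The same two are missing either way.

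The next SAP section, on ECGs (3.6.4), repeats the limits of protocol 9.2.3.4 in full. That makes a slip in carrying over the vital-sign list more likely than a deliberate removal, though the documents do not say which it was.

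**2. What the retained SBP row still catches**

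A fall of more than 25% from baseline B means a reading below 0.75 × B. This covers every reading below 90 when 0.75 × B ≥ 90, that is, when B ≥ 90/0.75 = 120 mmHg.

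For B from 90 to below 120, readings from 0.75 × B up to just under 90 are missed:

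- B = 118: 0.75 × 118 = 88.5. A reading of 89 is a fall of 29/118 = 24.6% and is not counted.
- B = 110: 0.75 × 110 = 82.5. A reading of 89 is a fall of 21/110 = 19.1% and is not counted.
- B = 90: 0.75 × 90 = 67.5. Readings from 67.5 to just under 90 are not counted.

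A patient with baseline SBP already below 90 would not enter the numerator, because the SAP requires a normal baseline on the criterion. The documents give no baseline SBP distribution, so the number of patients between 90 and 120 cannot be stated.

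**3. What catches a low heart rate**

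No threshold row does. The SAP table has no relative heart-rate criterion to overlap with the missing limit of 50, and SAP 3.6.4 sets no limit for heart rate from the ECG, which is only summarized.

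**4. The BMI row**

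Protocol 6.3.1 and Appendix A place BMI at Visit 1 (Day 1) only, with dosing after the other assessments that day. The visit lists in protocol 6.3.2 to 6.4.2 include no BMI, weight or height. Weight does not come in through the vital signs either: "Vital signs include temperature, respiratory rate, heart rate, and blood pressure" (protocol 8.13).

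Scheduled post-baseline BMI values per patient = 0. The denominator under the SAP rule is therefore 0 of 12 in each group, or 0 of about 36 overall, and the percentage is undefined.

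**5. When vital signs are taken relative to dosing**

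Doses are on Days 1, 29 and 57, each after that visit's assessments (protocol 6.3.1, 6.3.5, 6.3.7). From Appendix A, on target days:

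- After dose 1, the next scheduled vital signs are at Visit 3: 15 − 1 = 14 days.
- After dose 2, at Visit 7: 57 − 29 = 28 days.
- After dose 3, at Visit 9: 85 − 57 = 28 days.

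**The case against.** The best defence is that little information is lost. SAP 3.6.3 still summarizes vital signs at every visit, SAP 3.1.4 includes minimum and quartiles in those summaries, and all measurements are listed. With 12 patients per group, any reading below 90 or below 50 can be found. ECG heart rate is summarized separately, and clinically significant abnormalities are recorded as adverse events. The >25% fall row also covers every SBP below 90 from a baseline of 120 or more. All of this stands. What is lost is a pre-specified count by arm, not the underlying data.

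A reader might infer that the omission hides hypotension around injection reactions. The documents do not support that. Scheduled vital signs on dosing days precede the injection, and the next ones come about 2 to 4 weeks later, so restoring the rows would not detect such events from scheduled data. Those events are left to the 1 to 2 hours of observation after each dose (protocol 5.6.1) and to adverse-event reporting.

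A reader might also infer that the BMI row can never be computed. That is too strong. SAP 3.1.2 allows unscheduled assessments into analysis windows, so an unplanned weight could supply a value. The denominator of 0 holds for scheduled data only.

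Finally, the sponsor may have meant to change the list. That is open to it, but section 5 would then have to say so.

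**Conclusion.** The inconsistency is real and should be corrected. SAP Table 1 omits 2 of the protocol's 6 vital-sign criteria, adds 1 that has a denominator of 0 from scheduled data, and sits beside a no-change statement that is incorrect. Followed literally, the SAP produces no low heart-rate count and only a partial count of SBP below 90, with the gap in patients whose baseline lies from 90 to below 120 mmHg.

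The consequence is limited to descriptive safety tables. The primary analysis, its alpha and its power are unaffected, and no data go uncollected because of it.

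The conclusion assumes that Table 1 is complete as it reads. It shows five whole parameter-and-criterion pairs, but section 3.6.3 has no list in prose to check them against. It also assumes that no post-baseline weight is planned outside the protocol's schedule.

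**What to change.** In SAP 3.6.3, Table 1, add the protocol's own SBP <90 mmHg and heart rate <50 beats per minute criteria and delete the BMI row. If the sponsor intends any departure from protocol 9.2.3.3, declare and justify it in section 5 in place of the current no-change statement. Keeping the BMI criterion would also need post-baseline weight to be scheduled in the protocol.

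The recommended version is a three-row edit to one table, with matching changes to the output programs. Blood pressure and heart rate are already collected at the scheduled visits, so no new data are needed, and the SAP is to be finalized only before database lock.

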3.6.4 Electrocardiograms

ECG interpretation (normal vs abnormal) will be summarized using frequency and percentage at each visit by treatment group. ECG intervals (ie, PR interval, QT interval, heart rate, and QTcF) will be summarized descriptively at each visit. The number and percentage of patients with exceeding pre-defined absolute and relative threshold values (PR interval >200 msec; QTcF >450 msec, >480 msec, and >500 msec; and QTcF increase from Baseline >30 msec and >60 msec) will be summarized. These threshold values are presented in Table 2.

When calculating the percentages for the criterion related to a threshold, the numerator will be the number of subjects with normal baseline with respect to the specific criterion and at least one post-baseline outlier value within the analysis period; and the denominator will be the number of subjects with a baseline and at least one post-baseline assessment within the analysis period.

Table 2 Pre-defined Threshold Value for ECG

PR interval	Criteria
-------------	----------

QTcF	>200 msec
QTcF	>450 msec
QTcF	>480 msec
QTcF	>500 msec
QTcF	Increase from Baseline >30 msec
QTcF	increase from Baseline >60 msec

3.6.5 Physical Examinations

Clinically significant new or worsening physical examination findings will be reported as AEs and will therefore be summarized as described for AEs.

3.6.6 Antibodies to Ziltivekimab

The immunogenic potential of Ziltivekimab will be assessed by summarizing the number and percentage of patients who develop detectable ADAs. ADA titers will be summarized descriptively for ADA positive samples, and the impact of ADA on PK will be assessed if data allows.

3.6.7 Bleeding Events

Bleeding events will be classified using the Thrombolysis in Myocardial Infarction (TIMI) Bleeding Classification.

Table 1 TIMI Bleeding Classification

Parameter	Criteria
Major	Intracranial hemorrhage or a ≥ 5 g/dL decrease in the hemoglobin concentration or a $\geq 15\%$ absolute decrease in the hematocrit
Minor	Observed blood loss: ≥ 3 g/dL decrease in the hemoglobin concentration or $\geq 10\%$ decrease in the hematocrit. No observed blood loss: ≥ 4 g/dL decrease in the hemoglobin concentration or $\geq 12\%$ decrease in the hematocrit
Minimal	Any clinically overt sign of hemorrhage (including imaging) that is associated with a < 3 g/dL decrease in the hemoglobin concentration or $< 9\%$ decrease in the hematocrit
All TIMI definitions take into account blood transfusions, so that hemoglobin and hematocrit values are adjusted by 1 g/dL or 3%, respectively, for each unit of blood transfused. Therefore, the true change in hemoglobin or hematocrit if there has been an intervening transfusion between 2 blood measurements is calculated as follows: $\Delta \text{Hemoglobin} = [\text{baseline Hgb} - \text{post-transfusion Hgb}] + [\text{number of transfused units}]$; $\Delta \text{Hematocrit} = [\text{baseline Hct} - \text{post-transfusion Hct}] + [\text{number of transfused units} \times 3]$.	

Tables will be generated for each of the TIMI Bleeding Classification parameters by treatment and in total. Bleeding events will also be listed.

4 ANALYSIS TIMING

4.1 Draft Analysis/Blinded Data Reviews

All investigators and patients will remain blinded throughout the study. Additionally, members of the study team including operations team, data management, and statistical team will also remain blinded until the final database lock.

After the last subject completes the last visit, the final database will be cleaned, locked and analysis will be performed. At this time, members of the study team will become unblinded to the subject treatment assignments.

Prior to database lock, the blinded team may perform a blinded data review using tables, figures, and listings.

4.2 Interim Analysis

No interim analysis is planned for the study.

4.3 Pre-Final Analysis

After the final database is locked and exclusions from analysis populations have been finalized, the randomized treatment assignments will be unblinded and the pre-final analysis will be generated. Pre-final TFLs will be provided approximately 4 weeks after final database lock.

4.4 Final Analysis

After all comments on the pre-final analysis have been resolved and the study database is declared final, the final analysis will be generated. Final TFLs will be provided approximately 1 week after the study database is declared final. If there were no changes to the pre-final analysis or the study database, the pre-final TFLs may be considered final. In addition to TFLs, Study Data Tabulation Model (SDTM) data and Analysis Data Model (ADaM) data along with associated files will be provided. Associated files may include annotated CRFs, SDTM specifications, SDTM programs, ADaM specifications, ADaM programs, TFL programs, and Clinical Data Interchange Standards Consortium (CDISC) Define packages for both SDTM and ADaM data.

5 CHANGES FROM PROTOCOL-SPECIFIED STATISTICAL ANALYSES

None.

6 PROGRAMMING SPECIFICATIONS

Analyses will be performed using SAS® version 9.3 or higher. All available data will be presented in subject data listings which will be sorted by subject and visit date as applicable. Detailed Programming Specifications will be provided in a separate document.

